1 PROTOCOL SUMMARY

1.1 Synopsis

Protocol Title: A Multicenter, Randomized, Double-blind, Vehicle-Controlled, Phase 2a Study of TER-101 2.75% Topical Ointment to Assess Efficacy and Safety in Subjects with Mild to Moderate Atopic Dermatitis

Short Title: A Phase 2a Study of TER-101 Topical Ointment in Subjects with Mild to Moderate Atopic Dermatitis

Rationale:

TER-101 is a cytosolic phospholipase A2 alpha (cPLA_{2α}) inhibitor currently in development for the treatment of inflammatory skin diseases, including atopic dermatitis (AD). This Phase 2a study will assess efficacy, safety, and tolerability of TER-101 (2.75% weight for weight [w/w]) ointment (TER-101 Ointment) with its vehicle (TER-101 Placebo Ointment) twice daily for 28 days in adult and adolescent subjects with mild to moderate AD.

Objectives and Endpoints:

OBJECTIVES	ENDPOINTS
Primary	

 To assess the efficacy of TER-101 (2.75% w/w) ointment vs. vehicle in subjects aged 12 – 65 with mild to moderate AD 	
Primary Efficacy Endpoints
 
 Percent change in EASI from baseline at Day 29 
Secondary Efficacy Endpoints
 
 Percent change in EASI from baseline over time Percent change in individual components of EASI (erythema, induration/papulation, excoriation, lichenification) and by region (head, trunk, UE, LE) from baseline over time EASI-75, EASI-50 responder analysis over time Absolute change in EASI from baseline over time Change in IGA from baseline over time Change from baseline WI-NRS at Days 15, 29 (WI-NRS captured on e-diary daily) Responder analysis: Reduction of ≥ 3 in subjects with baseline WI-NRS ≥ 4 Change in TBSA affected from baseline over time
Secondary	

 To assess the safety and tolerability of TER-101 (2.75% w/w) ointment vs. vehicle in subjects with AD 	
 Safety: TEAEs, SAEs, VS, ECGs, laboratories Tolerability: Scored by investigator at baseline and post-baseline visits on 4-point scale (0 = none; 3 = severe) to include subscores for erythema, burning/stinging, pruritus.

 To assess systemic exposure to TER-101 (2.75% w/w) ointment after BID treatment for 28 days 	
PK: systemic plasma trough levels of TER-101 on Days 15, 29

BID = twice daily; EASI = Eczema Area and Severity Index; EASI-50/75 = 50 or 75% reduction in EASI score from baseline; ECG = electrocardiogram; IGA = Investigator Global Assessment; LE = lower extremities; PK = pharmacokinetics; SAE = serious adverse event; TBSA = Total Body Surface Area; TEAE = treatment emergent adverse event; UE = upper extremities; VS = vital signs; WI-NRS = Worst Itch Numeric Rating Scale; w/w = weight for weight.

Overall Design:

This is a Phase 2a, randomized, double-blind, vehicle-controlled study assessing efficacy, safety, and tolerability of TER-101 (2.75% w/w) ointment versus its ointment vehicle applied topically twice daily during a 28 day treatment period in adolescent and adult subjects (age 12 – 65) subjects with mild to moderate AD. Subjects will be randomized 1:1 to receive either TER-101 (2.75% w/w) ointment or vehicle. Efficacy assessments will include changes in Eczema Area and Severity Index (EASI), Investigator Global Assessment (IGA), Worst Itch Numeric Rating Scale (WI-NRS), and Total Body Surface Area (TBSA) affected. Safety and tolerability assessments will include reported adverse events (AEs), laboratories, physical examinations, electrocardiograms (ECGs), and vital signs as well as a separate tolerability assessment of treated

areas. Systemic exposure will be determined by measuring trough TER-101 levels on Day 15 and Day 29/End of Trial (EOT). Photographs of representative areas of AD will be obtained at baseline, Day 15, and Day 29/EOT.

Disclosure Statement:

This is a study with 2 treatments that are subject- and investigator-blinded.

Number of Investigators and Study Sites:

Approximately 12 clinical research sites in the United States are expected to participate in this study.

Number of Subjects:

The study will enroll and randomize a total of approximately 60 subjects aged 12 - 65.

Diagnosis and Main Criteria for Inclusion:

Adolescent and adult subjects (age 12 – 65) with mild to moderate AD at baseline.

Major Inclusion Criteria

- Diagnosis of AD according to the Hanifin and Rajka criteria [Appendix 5, [Section 10.5](#)].
- AD disease duration of at least 6 months, with no change in treatment or severity for at least 4 weeks prior to screening.
- Overall IGA score of 2 (mild) or 3 (moderate) at baseline on a 5-point IGA scale.
- TBSA affected of between 2 and 30% at baseline.
- EASI \geq 5 at baseline.

Major Exclusion Criteria

- AD with clinical evidence of superinfection.
- Other dermatological conditions that require concomitant treatment, potentially cause diagnostic confusion with AD, or interfere with the study assessments. This may include excessive facial hair, tattoos.
- Known hypersensitivity to study drug or excipients, including polyethylene glycol (PEG) 400, PEG 4000, or propylene glycol.
- Treatment of AD with the following therapies within the washout periods specified prior to baseline:
 - Topical corticosteroids including over the counter (OTC) corticosteroids – 1 week.
 - Topical calcineurin inhibitors, phosphodiesterase 4 (PDE4) inhibitors, topical antihistamines – 2 weeks.
 - Systemic or topical antibiotics – 2 weeks.

- Initiation of systemic antihistamines or tricyclic antidepressants (TCAs) – 2 weeks
 - Subject on a stable dose of antihistamines or TCAs at screening may be enrolled
- Systemic immunosuppressants (systemic corticosteroids, cyclosporine, mycophenolate, methotrexate, azathioprine, etc) – 4 weeks.
 - Nasal, ophthalmic, or inhaled corticosteroids for indications such as rhinitis, allergic conjunctivitis, or asthma/chronic obstructive pulmonary disease are permitted.
- Biologics (dupilumab, other) – 12 weeks.
- Investigational biologic agents – 12 weeks or 5 half-lives of the drug, whichever is longer.
- Investigational nonbiologic agents – 4 weeks or 5 half-lives of the drug, whichever is longer.
- Use of complementary and alternative medications and supplements including St. John's wort, cannabidiol (CBD) (oral or topical) – 2 weeks.
- Systemic treatment with potent inhibitors or inducers of CYP3A4 – 2 weeks.
- Receipt of artificial or natural light therapy such as phototherapy (ultraviolet B [UVB], psoralens + ultraviolet A [PUVA]), regular use of a tanning booth/parlor, lasers, red light or blue light, or tanning within 4 weeks of baseline.
- Women of childbearing potential (WOCBP) who are pregnant or intending to become pregnant during the course of the study, lactating, or unwilling or unable to use an acceptable method of contraception as defined in [Section 10.8](#) for the duration of the study.
- Males with female partners of childbearing potential who are not using or willing to use an acceptable method of contraception as defined in [Section 10.8](#). Male subjects should refrain from sperm donation for 90 days after study completion.
- Receiving hormonal therapy (eg, estrogen, testosterone) for gender reassignment.
- Current or recent history (within 12 weeks of the Screening Visit) of severe, progressive, or uncontrolled renal, hepatic, hematological, gastrointestinal, metabolic, endocrine, pulmonary, cardiovascular, psychiatric, or neurological disease per investigator opinion.
- Has clinically relevant abnormalities on the screening ECG, including long QT (eg, corrected QT [QTc] \geq 480 msec).
- Is immunocompromised.
- Has recently (within 4 weeks of the Screening Visit) received live vaccine(s). Enrolled subjects should not receive live vaccines during the study and for 30 days after study discontinuation.
- Known history of hepatitis B virus, hepatitis C virus or human immunodeficiency virus (HIV) OR a recent (within 4 weeks of the Screening Visit) known infection with SARS-CoV-2 (coronavirus disease 2019 [COVID-19]).
- History of malignancy in the previous 5 years except for adequately treated nonmelanoma skin cancers or cervical carcinoma in situ.
- Recent (within 12 months of screening) history of substance abuse or unwilling to follow protocol restrictions on alcohol consumption ([Section 5.3.2](#)).

Treatment Groups and Duration:

At baseline, eligible subjects will be randomized to TER-101 (2.75% w/w) ointment or vehicle to be applied topically twice daily for 28 days to all affected areas. The study will include up to a 35-day screening period prior to enrollment/Baseline Visit and a 28-day active treatment period. Subjects will apply the first dose of medication at the baseline visit (Day 1) and will apply dispensed clinical trial ointment to the areas identified at baseline throughout the 28-day treatment period.

AD assessments will consist of the EASI, IGA, TBSA affected and a daily recording of the WI-NRS. EASI, IGA, and TBSA are strongly recommended to be performed by the same qualified evaluator throughout the study and particularly for baseline and Day 29/EOT visits.

Safety assessments will include reported AEs/treatment emergent AEs (TEAEs), periodic vital signs, physical examinations, pregnancy tests, ECGs, and clinical laboratory evaluations.

Tolerability will be assessed at baseline (pre-dose), 15 minutes post-baseline dose, and Days 15 and 29 by the investigator and include assessments for erythema, stinging/burning, and pruritus.

If severe local application site AEs or scores of 3 on two or more tolerability subscores arise with BID dosing, treatment will be withheld to the affected area. When the local AE(s) has resolved or tolerability score returns to baseline, subjects may restart application to the affected area once daily. See [Section 6.2](#) of protocol.

Pharmacokinetics: Trough levels on Days 15, 29.

Other Assessments:

Photography of representative lesions will be taken at baseline, Day 15, and Day 29. The same areas will be photographed throughout the study under the same conditions.

Statistical Methods:

The sample size is based on a clinical rather than statistical rationale. Approximately 60 subjects are planned to be enrolled and randomized, considering a potential 15% dropout rate, to yield approximately 50 subjects completing the study. Statistical analyses will be exploratory to assess the drug's activity and potential for further study.

All randomized subjects who receive at least 1 application of the study treatment will be included in the Safety Analysis Set (SS). All randomized subjects who receive at least 1 application of the study treatment and have 1 post-baseline efficacy assessment will be included in the Efficacy Analysis Set (ES). All subjects in ES without major protocol deviations will be included in the Per Protocol Efficacy Analysis Set (PPES).

The primary efficacy endpoint (percent change in EASI total score) will be analyzed using a mixed model for repeated measures (MMRM). The model will include fixed effects for study treatment (TER-101 [2.75% w/w] ointment or vehicle), visit (Day 15, Day 29), and treatment-

by-visit interaction with visit as the repeating factor, subject as a random effect, and baseline score as a covariate. The treatment p-value (TER-101 [2.75% w/w] ointment vs. vehicle), treatment difference, and 95% confidence limits from the model will be presented for the percent change in EASI from baseline at Day 29. Sensitivity analyses will include analysis of covariance (ANCOVA) at each timepoint. The impact of dropouts and missing data on results for the primary endpoint will be explored using the last value carried forward (LOCF) and multiple imputation methods, as appropriate.

Secondary efficacy endpoints that are continuous variables (percent change in EASI over time, and absolute change in EASI component scores, IGA, TBSA, and WI-NRS) will also be analyzed using the MMRM model as described above. The treatment difference in response rates (75% reduction in EASI score [EASI-75], 50% reduction in EASI scores [EASI-50]) at each visit will be evaluated using a logistic generalized linear mixed model (GLMM) for binary data, with fixed effects for treatment, visit, and treatment by visit interaction. The odds of response will be reported from the model together with the 95% confidence interval. (Note: If repeated measures models fail to converge, the response proportions will be analyzed using the generalized Cochran-Mantel-Haenszel test, stratified by baseline IGA.) The proportion of WI-NRS responders (defined by a reduction of ≥ 3 in subjects with baseline WI-NRS ≥ 4) will be analyzed using a chi-square test.

Time to onset of response (EASI 75, EASI-50) will be estimated using the Kaplan-Meier method, with treatment comparisons based on the logrank test. Subjects who do not achieve response criteria will be censored on the day of last assessment.

Given the exploratory nature of this study, p-values from all significance tests will be reported without adjustment for multiplicity.

Descriptive statistics will include line graphs of % change in EASI scores and bar charts of response rates at each time point, to describe the effect of treatment over time.

The number and percentage of subjects reporting TEAEs, coded using the Medical Dictionary for Regulatory Activities, will be summarized by treatment, by treatment related, by maximum severity, by leading to study treatment or study withdrawal, and by serious TEAEs.

[figure not shown]
Changes from baseline in laboratory measurements, ECG assessments, and vital signs will be summarized using descriptive statistics.

Tolerability scores and pharmacokinetic (PK) parameters will be summarized by treatment and visit.

Data Monitoring Committee: None.

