2.3 Benefit/Risk Assessment

TER-101 was safe and well tolerated when administered as a topical ointment (1.0% w/w) twice daily for up to 2 weeks to healthy volunteer subjects (n=8) and patients (n=28) with moderate to severe AD. The most common treatment emergent adverse events (TEAEs) in TER-101 treated subjects were local application site events including pruritus, dry skin, and dermatitis. The majority of reported TEAEs in healthy volunteers or subjects with AD were mild to moderate in

severity. Three of 10 subjects with moderate to severe AD randomized to the vehicle arm withdrew due to TEAEs related to lack of efficacy. No healthy volunteers or subjects with AD treated with TER-101 withdrew from the study. There were no clinically significant safety concerns identified in vital signs, physical examinations, electrocardiograms (ECGs), or clinical laboratory assessments.

In this small study, there was no statistically significant difference in the primary efficacy analysis (percentage change from baseline in Eczema Area and Severity Index [EASI] score at Week 2) or in a sensitivity analysis using multiple imputation, between the TER-101 and placebo groups. In the sensitivity analysis using last observation carried forward, there was evidence of a trend towards a larger decrease in EASI scores and other efficacy assessments in the TER-101 compared with the placebo group. This result was also supported by the worst-case imputation sensitivity analysis. Three patients in the TER-101 group were assessed as EASI-75 (75% reduction in EASI score from baseline) responders. No patients in the placebo group met this definition. A trend towards greater improvement in the TER-101 group was also evident in the Patient Global Impression of Change assessment.

Teres Bio anticipates the most likely TEAE in the Phase 2 upcoming study will be local application site TEAEs including pruritus, dry skin, stinging/burning, pain, or dermatitis including atopic dermatitis. The protocol includes rules for treatment cessation in the event that subjects develop severe local TEAEs or high scores on the tolerability assessments. Once local AEs have abated, treatment may be re-initiated once daily. Teres Bio believes that the accrued clinical safety and preliminary efficacy data support a favorable benefit-risk profile for the proposed protocol and that appropriate monitoring and stopping rules have been included in the planned study design.

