3.2 ANALYSIS POPULATION AND DISPOSITION OF SUBJECTS

3.2.1 Data Sets Analyzed

For purposes of analysis, the following populations are defined

Population	Description
Efficacy analysis set (ES)	All randomized subjects who receive at least 1 application of the study treatment and have at least 1 post-baseline efficacy assessment. The treatment group as assigned (randomized to) will be used for analyses.
Per protocol efficacy analysis set (PPES)	All subjects in ES without major protocol deviations that impact the interpretation of the results. The treatment group for the first application will be used for analyses.
Safety analysis set (SS)	All randomized subjects who receive at least 1 application of the study treatment. If any TER-101 was applied, then the subject will be summarized under TER-101 treatment group.
PK analysis set (PKS)	All subjects in SS with at least 1 blood draw to measure TER-101.

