3.6 EFFICACY ANALYSIS

All efficacy analyses and summaries will be performed on the ES by randomized treatment group. Additional analyses based on PPES will be specifically mentioned.

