3.6.1 EASI Analyses

For each visit (baseline, Day 15, Day 29), the following analyses will be performed. All analyses will be based on the ES.

- Descriptive statistics (n, mean, Std Dev, median, minimum, and maximum) will be provided for the per-subject EASI total score (continuous), change from baseline, and percent change from baseline in EASI total score.
- Descriptive statistics (n, %) will be provided for the number and percentage of subjects who achieve EASI-50 (i.e., ≥50% reduction from baseline) and EAST-75 (i.e., ≥75%).

Descriptive statistics (n, mean, Std Dev, median, minimum, and maximum) will be provided for the per-subject EASI by region (head, trunk, upper extremity [UE], lower extremity [LE]), change from baseline, and percent change from baseline values. Treatment group comparisons

in percent change from baseline in EASI total score will be analyzed using a mixed model for repeated measures (MMRM). The model will include fixed effect for study treatment (TER-101 2.75%, vehicle), visit day (Day 15, Day 29), and treatment-by-visit interaction, with visit as the repeating factor, subject nested within the investigational site as a random effect, and baseline score as a covariate. The variance-covariance matrix will be assumed to be unstructured. If the procedure does not converge then the replacement of variance-covariance matrix will be explored in the order of Toeplitz, first-order autoregressive, compound symmetric. The treatment p-value (TER-101 2.75% vs. vehicle), treatment difference, and 95% confidence limits from the model will be presented for the percent change from baseline in EASI at Day 29. Similarly, the treatment difference (TER-101 2.75% vs. vehicle) and 95% confidence limits will be presented for Day 15 as well. Line graphs of least squares mean in percent change from baseline of EASI scores will be presented for Day 15 and Day 29. These treatment group comparisons will be repeated for the PPES.

The following sensitivity analyses will be conducted for the percent change from baseline in EASI total score at Day 29 to explore the impact of dropouts and missing data at Day 29.

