- Last value carried forward (LOCF): for timepoint Day 29, if missing, the last available post baseline EASI total score will be carried forward to the timepoint. After this imputation, an analysis of covariance (ANCOVA) will be used for analyzing the treatment effect at Day 29. The treatment group will be the fixed effect and baseline score will be the covariate. The treatment difference, 95% confidence limits, and p-value will be presented.
- Return to baseline: missing Day 29 value will be imputed based on the baseline value for the patient, with variance adjustment of the Day 29 EASI total score. That is, the missing data will be imputed with values from Normal distribution $N(\text{baseline}_i, \sigma_k^2)$; i = i th subject, where σ_k^2 is the variance estimate of treatment k at Day 29. Five hundred (500) imputation will be implemented. ANCOVA model will be used for each imputation. The results from all imputed datasets will be combined using Rubin's combination rule (PROC MIANALYZE).

In addition, the percent change from baseline in EASI scores and the absolute change from baseline in EASI total score by each region will be analyzed using the MMRM model, as described above. In each case, the treatment p-value (TER-101 2.75% vs. vehicle), treatment difference, and 95% confidence limits from the model, will be presented.

The effect of treatment on response rates (EASI-75, EASI-50) at each visit will be evaluated using a logistic generalized linear mixed model (GLMM) for binary data. The model will include fixed effect for treatment, visit and treatment-by-visit interaction, with subject nested within the investigational site as a random effect. The treatment p-value (TER-101 2.75% vs. vehicle), treatment odds ratio, and 95% confidence limits from the model, will be presented. [Note: In the event of model non-convergence, the response proportions will be analyzed using the Cochran-Mantel-Haenszel test, stratified by baseline IGA.] Bar charts of the response rates at Day 15 and Day 29 will be presented by treatment groups for each response rate (EASI-75, EASI-50).

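### The return-to-baseline analysis needs only a baseline EASI, yet it is confined to the efficacy set, so treated subjects with no post-baseline efficacy record are left out of it

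*Protocol*

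**What the plan says.** **Efficacy set (ES).** SAP 3.2.1 defines it as "All randomized subjects who receive at least 1 application of the study treatment and have at least 1 post-baseline efficacy assessment". The Protocol has the same rule in 9.3 and in the synopsis ("have 1 post-baseline efficacy assessment will be included in the Efficacy Analysis Set (ES").

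**Where it applies.** SAP 3.6 states: "All efficacy analyses and summaries will be performed on the ES by randomized treatment group". SAP 3.6.1 repeats this for the EASI section: "All analyses will be based on the ES".

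**Sensitivity analyses.** SAP 3.6.1 gives two for Day 29, and their purpose is "to explore the impact of dropouts and missing data at Day 29". LOCF carries forward a post-baseline EASI and so needs one. Under return-to-baseline, a "missing Day 29 value will be imputed based on the baseline value for the patient". The value is drawn from a normal distribution centred on the subject's own baseline, with the arm's Day 29 variance. There are 500 imputations, each analysed by ANCOVA and then pooled.

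**What counts as an efficacy assessment.** Protocol 4.1 lists EASI, IGA, WI-NRS and TBSA. WI-NRS is recorded daily at home (Protocol 8.2.4, SAP 2.4.2.3), and the Day 1 score is its baseline (SAP 3.1). Neither document says which of the four is needed for ES entry.

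**When EASI is measured.** After baseline, the first scheduled EASI is at Day 15 ± 3, because Day 8 is a remote contact (Schedule of Activities). Subjects who leave early are to have the Day 29 assessments at an early termination visit (Protocol 6.6.1, 7.1, 7.2), though 7.2 asks for that visit only where it can be done.

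**The concern.** ES membership depends on something that happens after randomization. For the MMRM and LOCF this costs nothing, since a subject with no post-baseline EASI gives neither of them an outcome. Return-to-baseline is different. It is the only planned analysis that could use such a subject, and the only form in which the SAP carries out the multiple imputation foreseen in Protocol 9.4.6. Confining it to the ES gives up that advantage for subjects who leave no efficacy record after baseline.

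Site staff apply the first dose at the Baseline Visit, so nearly every randomized subject will be treated. The post-baseline condition is thus the one that can exclude. If more subjects are excluded from one arm than from the other, the sensitivity analysis no longer compares the arms as randomized. Omitting TER-101 subjects would flatter TER-101; omitting vehicle subjects would understate it.

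The wording adds an oddity. Taken literally, one itch-diary entry decides whether a subject with no post-baseline EASI enters an EASI analysis.

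**Working it through.** **1. Who is left out.** Treated subjects with a baseline EASI and no Day 29 EASI fall into three groups:

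| Post-baseline data | In ES, literal wording | In ES if an EASI is required | Return-to-baseline computable? |
|---|---|---|---|
| An earlier post-baseline EASI | yes | yes | yes |
| No EASI, but a diary score after Day 1 | yes | no | yes |
| No efficacy record at all | no | no | yes |

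The third group is omitted on either reading. The second is omitted only if the assessment must be an EASI.

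**2. How many.** The planning figures (Protocol 9.2, SAP 1.2) are about 60 randomized, 15% dropout and about 50 completers.
- Check: 50 / 0.85 = 58.8, rounded up to 59, against 60 planned. Forward, 60 × 0.85 = 51, against 50 planned. Both agree with the approximate figures stated.
- Implied dropouts: 60 × 0.15 = 9.
- The number with no qualifying record is not given. It lies between 0 and about 9, and reaches 9 only if every planned dropout lacks one.

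**3. Shift per omitted subject.** Allocation is 1:1, so take 30 treated per arm. An imputed value is centred on the subject's own baseline, so its expected percent change is 0. If k subjects are omitted and the rest of the arm has mean μ, restoring them gives μ(1 − k/30), a shift of |μ| × k/30. The arm means are assumptions, as the documents give no effect size or SD.
- k = 1: 30 × 1/30 = 1.0 point; 50 × 1/30 = 1.7 points.
- k = 3: 3.0 points; 5.0 points.

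**4. Effect on the contrast.** Assume −50% on TER-101 and −30% on vehicle, a difference of −20 points with the subjects omitted. With them restored, the difference is −50(1 − kT/30) + 30(1 − kV/30), where kT and kV are the numbers omitted from TER-101 and vehicle:

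| Omitted, TER-101 / vehicle | Difference when restored |
|---|---|
| 1 / 1 | −19.3 |
| 2 / 2 | −18.7 |
| 3 / 0 | −15.0 |
| 0 / 3 | −23.0 |
| 5 / 4 | −15.7 |
| 9 / 0 (outer limit) | −5.0 |
| 0 / 9 (outer limit) | −29.0 |

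**5. Set against the noise.** For an assumed SD of 30 to 50 points, the standard error of the difference is SD × √(2/30), or about 7.7 to 12.9 points. One omitted subject (1.0 to 1.7 points) is then roughly 0.1 to 0.2 of a standard error.

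**The case against.** A reader might infer that the return-to-baseline analysis leaves out early dropouts in general. The documents do not support that. ES entry asks for any efficacy assessment, the itch score is one, it is recorded daily, and diary completion is checked at the Day 8 contact. Subjects stopping for tolerability, adverse events or rescue are meant to have an early termination visit that includes EASI. SAP 3.1 even has a Day 2 to Day 11 window in which an early EASI would fall. On the literal wording, most early dropouts would stay in the ES and be imputed.

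A reader might also take the earlier study as evidence of biased exclusion. Protocol 2.3 reports that "Three of 10 subjects with moderate to severe AD randomized to the vehicle arm" withdrew, for events related to lack of efficacy, and that no TER-101 subject did. It does not say that those subjects lacked post-baseline assessments, and they had more severe disease than this trial enrols. If the pattern recurred among omitted subjects, the omission would understate TER-101.

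Three further points are fair:
- Keeping one population means that return-to-baseline differs from the primary only in its missing-data handling and model.
- Protocol 9.7 already requires missing efficacy data at Days 15 and 29 to be reported by arm with reasons, and SAP 3.2.3 tabulates discontinuations.
- The trial is exploratory, and no decision rule hangs on this analysis.

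These points reduce the concern without removing it. The early termination visit will sometimes not happen, and a subject lost to follow-up may have neither a visit nor a diary entry. A count of missing data does not show what those subjects do to the Day 29 contrast. The term that decides ES entry also remains undefined.

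**Conclusion.** The point holds in limited form and is minor. A stated rule removes some treated subjects from a dropout analysis that could include them. On the literal wording these are only subjects with no WI-NRS entry after Day 1 and no later clinic assessment. If an EASI is required, they are all those with no post-baseline EASI. The number could be zero and is at most about 9 of 60.

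The size of 1.0 to 1.7 points per omitted subject rests on 30 treated per arm and assumed arm means of −30% to −50%. A shift of 3 to 5 points needs a further assumption, that three subjects are lost without any qualifying record and all from one arm. The direction depends on which arm loses more. The documents support neither a fixed bias for or against TER-101 nor any effect on the primary MMRM or on LOCF.

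**What to change.** In SAP 3.6.1, state that return-to-baseline is run on all randomized subjects who were treated at least once and have a baseline EASI, by randomized arm, whether or not any post-baseline assessment exists. Keep the ES for the MMRM and LOCF. Report per arm how many subjects enter with no post-baseline EASI. For this analysis it then no longer matters which assessment qualifies a subject for the ES.

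The cost is one sentence and one extra count in a table, with no new data. The downside is that the sensitivity analysis uses a slightly larger set than the primary, so the two differ in population as well as in missing-data handling. Its estimate is also slightly more conservative for the arm with more early losses. Make the change before unblinding, so that the choice of set cannot look driven by the losses seen in each arm.
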